#### 2. Concomitant medication (CM) start and end date imputation

The imputation of missing medication start and/or end dates is performed for the following reasons:

- To determine if a medication is a prior medication or a concomitant medication.
- To determine if treatment with the medication satisfies any of the medication-related exclusion criteria #18, #19, #20, #21, #22, #23, #24, #25, and #27 for subject eligibility.

The medication start and end dates are separated into 3 different data fields, including day, month, and year. Completely missing medication start and/or end date (i.e., missing day, missing month, and missing year) will not be imputed. Partially missing medication start/end date will be imputed according to treatment start date. The rules on how to determine if a medication is a prior medication only or both prior and concomitant medication and to determine if subjects violated any protocol specified medication-related exclusion criteria are specified below.

The prior and concomitant medications data listings will display all data as collected; imputed values will not be shown.

#### • Medication Start Date Imputation

- a) If medication start year is missing, then no imputation
- b) If medication start year is reported while medication start month and day are missing, then medication start month/day = '01JAN'

c) If medication start year and month are reported while medication start day is missing, then medication start day = '01'

## • Medication End Date Imputation

- a) If medication start date and medication end date are completely missing; or medication end date is completely missing while medication start date is either a complete date or partially missing and the observed/imputed medication start date < treatment start date, then no imputation:
  - If Ongoing = Yes, the medication is considered to be both prior and concomitant medication
  - If Ongoing = No or missing, the medication is considered to be a prior medication only
  - Subject will be considered as violating the medication-related exclusion criteria if the medication is one of the prohibited medications according to the medication-related exclusion criteria.
- b) If medication start date is completely missing while medication end date is partially missing; or medication end date is partially missing while medication start date is either a complete date or partially missing and the observed/imputed medication start date < treatment start date, then the missing medication end date will be imputed as follows:

	MMM Missing	MMM < TRT Month	MMM = TRT Month	MMM > TRT Month
YYYY < TRT Year	31DEC	Last day of MMM	Last day of MMM	Last day of MMM
YYYY = TRT Year	TRTDT *	Last day of MMM	TRTDT *	01MMM
YYYY > TRT Year	31JAN	Last day of MMM	Last day of MMM	Last day of MMM

\* If Ongoing = Yes, then no imputation.

Where: YYYY = Medication end year; MMM = Medication end month; TRT Year = Treatment start year; TRT Month = Treatment start month; and TRTDT = Treatment start date.

- The observed and/or imputed medication end date will be used to determine if a medication is a prior medication only; or is both a prior and a concomitant medication.
- If the medication is one of the prohibited medications according to the medicationrelated exclusion criteria, the observed and/or imputed medication end date will also be used to determine if a subject meets any medication-related exclusion criteria.
- c) If the medication start date is either a complete date or partially missing with the observed/imputed medication start date >= treatment start date, then no imputation for medication end date, and:
  - The medication is considered to be a concomitant medication only.
  - Subject doesn't meet any medication-related exclusion criteria.

## 3. Other date imputations

Any event with a partial date that requires imputation but has no specific imputation rule will be imputed as follows:

- If the day is missing, then impute the day as '01'
- If the month is missing, then impute the month as 'JUL'
- If the imputation of a start date causes the start date to be post the non-missing end date, then the start date will be imputed as the end date.
- If the imputation of a start date causes the start date to be prior to the start of treatment (but the event should happen post-baseline), then the start date will be imputed as "treatment start date + 1."

Any date cannot be imputed past the date of death. When this happens, the date will be imputed as the date of death.

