## **Adverse Events of Special Interest**

An adverse event of special interest (AESI) is an AE that is designated to be of special medical or scientific interest to the Sponsor. There are four major categories of AESIs as follows:

- Injection site reaction AEs -- Skin reaction AEs at the injection site
- Skin AESIs -- AEs of eschar, ulcer, or non-healing wounds at the injection site
- Hypersensitivity AESIs -- TEAEs in the Hypersensitivity Standardized MedDRA Query (SMQ narrow)
- Other AESIs:
  - Orthostatic hypotension

Study BA058-05-019 SAP

- Tachycardia
- Nausea
- Hypercalcemia
- Hypercalciuria
- Hypophosphataemia

The MedDRA PTs, High Level Terms (HLT), and SMQs used to identify the AESIs are stored in the study folder in the Biometrics SAS Environment.

An overall summary of the treatment emergent AESIs will be provided, in which the number of subjects with any adverse events, number of subjects with any TEAEs, number of subjects with any treatment-related TEAEs, number of subjects with any severe TEAEs, number of subjects with any treatment-related severe TEAEs, number of subjects with any serious TEAEs, number of subjects with any treatment-related serious TEAEs, number of subjects with any TEAES leading to study drug withdrawal, number of subjects with any TEAEs leading to study drug interruption, number of subjects with any TEAEs leading to study discontinuation, and number of subjects with any TEAEs leading to death will be summarized by treatment group.

The treatment emergent AESIs will be summarized by PT and SOC for each of the AESIs. Summary of the onset time and duration of the treatment emergent AESIs will be provided by treatment group using descriptive statistics (number of subjects, mean, SD, median, interquartile range, minimum and maximum). The number of subjects in each of the onset time groups (1 day, 2-3 days, 4-7 days, 8-15 days, 16-29 days, 1 to <2 months, 2 to <6 months, 6 to <10 months, and >=10 months) and duration groups (1 day, 2-3 days, 4-7 days, 8-15 days, 16-29 days, and >= 30 days) will also be summarized by treatment group.

To evaluate the relationship between AESIs and the antibody status, the incidence of treatment emergent AESIs will also be summarized by antibody status (ADA-, ADA+/Nab+, ADA+/Nab-, All ADA+, and Overall), SOC, and PT for the abaloparatide SC group.

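### SAP Appendix D has no rule for partial adverse event end dates, and the catch-all that would fill the gap can place the end before onset, giving zero or negative AESI durations

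*SAP*

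**What the plan says.** Appendix D of the SAP has three parts. D.1 is confined to adverse event start dates; an end date appears there only as a fallback for a start date that is still missing. D.2 deals with medication start and end dates. D.3 takes whatever remains: "Any event with a partial date that requires imputation but has no specific imputation rule will be imputed as follows". Its first rule is "If the day is missing, then impute the day as" 01, and its second sets a missing month to July.

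D.3 then adds safeguards. Two act on an imputed start date. One begins "If the imputation of a start date causes the start date to be post the non-missing end date", and the other moves forward a start date that would fall before treatment although the event belongs after baseline. The third applies to every date: "Any date cannot be imputed past the date of death". That is an upper limit only.

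The output that needs an end date is in SAP 4.5.3, Adverse Events of Special Interest: "Summary of the onset time and duration of the treatment emergent AESIs will be provided by treatment group". It is to show the mean, SD, median, interquartile range, minimum and maximum, and counts in six duration groups: 1 day, 2-3, 4-7, 8-15, 16-29, and 30 days or more. The SAP gives no formula for AESI duration.

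**The concern.** A date rule that feeds a duration has to keep the end on or after the start. D.3 protects that order when the start is imputed but not when the end is. Take an event with onset on 15 March and an end recorded only as March. D.3 gives an end of 1 March, and end minus onset plus one is 1 - 15 + 1 = -13 days. That value belongs to none of the six groups, yet it enters the mean and the minimum unless someone removes it by a rule that the SAP does not contain.

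Some partial stop dates are foreseeable. From Month 3 the clinic visits are three months apart, so a stop date may rest on recall, and the SAP already provides for partial onset dates. At stake is whether the AESI duration table can be read as it stands. The events concerned include injection site reactions, nausea, tachycardia and orthostatic hypotension, some of which may be short.

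**Working it through.** The plan states no figure for AESI duration or for the share of partial end dates, so there is nothing to reproduce. The check applies D.3 to every possible end date.

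**Inputs from the SAP**
- Missing day becomes 01; missing month becomes July, so with both missing the date is 1 July (Appendix D.3).
- No lower limit at onset (Appendix D.3).
- Duration groups start at 1 day (4.5.3).

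**Assumptions**
- The true end date is uniform over the 365 days of a non-leap year, and onset is fully known.
- Duration = end - onset + 1, the form that SAP 4.5.1 uses for drug exposure.

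**Case A: only the day is missing.** The imputed end is early by (day of month - 1).
- Mean shortfall: a month of n days contributes n(n - 1)/2. The total is 7 × 465 + 4 × 435 + 378 = 5,373, and 5,373/365 = 14.7 days, with a range of 0 to 30.
- The imputed end precedes onset when the day of the month on which the event ended exceeds the true duration d. For d up to 28 the number of such end dates is 365 - 12d.
- The duration group stays correct only when the shortened value remains in the same band.

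| True duration (days) | Imputed end before onset | Correct group kept |
|---|---|---|
| 1 | 353/365 = 97% | 12/365 = 3% |
| 3 | 329/365 = 90% | 24/365 = 7% |
| 7 | 281/365 = 77% | 48/365 = 13% |
| 14 | 197/365 = 54% | 84/365 = 23% |
| 29 | 18/365 = 5% | 168/365 = 46% |
| 45 | 0 | 192/365 = 53% |

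In 12 of the 365 cases for each of the durations 1, 3, 7 and 14 days, the result is exactly zero; the rest of those before onset are negative.

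**Case B: month and day are missing.** The imputed end is 1 July, day 182 of the year. The error is 182 minus the true day of the year.
- Range: from 182 - 365 = -183 to 182 - 1 = +181 days. Mean: 182 - 183 = -1 day.
- Too long in 181/365 (50%) and too short in 183/365 (50%).
- Imputed end before onset in (184 - d)/365: 183/365 = 50% for 1 day, 170/365 = 47% for 14 days, and 94/365 = 26% for 90 days.

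**Alternatives in Case A (mean error in days)**

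| Rule | 1 day | 7 days | 14 days | 29 days |
|---|---|---|---|---|
| 01 of the month, raised to onset if earlier | 0 | -5.3 | -10.0 | -14.7 |
| Last day of the month | +14.7 | +14.7 | +14.7 | +14.7 |
| Midpoint from the later of onset and the 1st to month end | +7.1 | +4.5 | +2.1 | -0.2 |

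None of the three produces a duration below 1 day.

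**The case against.** The strongest reply is that D.3 may not apply. It covers only a partial date that requires imputation, and SAP 3.11 names only adverse event onset and medication start when it introduces Appendix D. The sponsor could leave a duration missing when the end date is partial. This stands as a caution: applying D.3 is the natural reading, because 4.5.3 needs the date and no other rule reaches it, but it is an inference. It does not remove the gap, since the SAP does not say that such events are left out either.

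A second reply is that the effect is small. It stands. Safety is largely descriptive under SAP 4.5, the same rule applies in both arms, and missing data are queried (Protocol 9.7). Calcium, orthostatic blood pressure, heart rate and local tolerance have separate measured summaries that do not use event end dates.

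A reader might also infer more than the documents support:
- **That every imputed duration is too short.** This fails when the month is missing. For a true duration of 14 days, 365 - 170 = 195 end dates give a positive duration, and 181 of those 195 (93%) are too long. Even in Case A, the direction in the final table depends on what is done with the non-positive values. If they were dropped and durations were exponential (an assumption), the mean of those kept would be almost unchanged, because mainly short events drop out.
- **That D.2 treats end dates in the opposite way.** D.2 serves to classify medications as prior or concomitant and to check eligibility. Its table, introduced by "then the missing medication end date will be imputed as follows", uses the last day of the month in many cells, but the first of the month or the treatment start date in others. It imputes no end date for a medication started on or after first dose.
- **That fracture dates or treatment-emergent counts are at risk.** Fractures are assessed at each treatment visit and must be documented with images and reports, so a year-only date is unlikely. Treatment-emergent status rests on onset and severity. The D.1 fallback needs a non-missing end date, and nothing says that an imputed one counts.

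**Conclusion.** The gap is real and minor. Appendix D has no rule for a partial adverse event end date, and the one rule that can reach it allows an end before onset. With only the day missing, the average shortfall is 14.7 days; short events are hit hardest, and most events lasting 1 or 7 days would get a zero or negative duration. With the month missing, the error can reach about six months in either direction and averages about -1 day.

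These figures are conditional on an end date being partial. They also assume that D.3 is applied, that end dates are uniform over the year, and that duration counts both end days. The documents do not give the number of partial end dates, so the effect on the table as a whole cannot be stated. The effect is confined to the descriptive AESI duration summaries. The bone density analyses do not use these dates.

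**What to change.** Add an adverse event end-date rule to Appendix D.1, in one of two forms.

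- **Impute with limits.** Never set the imputed end before onset, and cap it at last contact or death. One suitable choice is the midpoint between the later of onset and the first possible date, and the last possible date.
- **Do not impute.** State that partial end dates are left as they are and that those events are omitted from the duration summary, with their number shown.

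In either case, give the duration formula in 4.5.3, and flag any imputed durations in the table.

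The cost is a sentence or two in the SAP and a little programming. The bounded midpoint overstates short durations by a few days (about 7, 4 and 2 days for true durations of 1, 7 and 14 days when only the day is missing). A floor at onset alone would remove the impossible values but leave longer events about 15 days short on average. The last day of the month overstates by the same amount. Omitting the events avoids both errors but loses those durations from the table.
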